7.5.2 Secondary Endpoints

7.5.2.1 Progression Free Survival (PFS)

Progression-free survival (PFS) is defined as the time from randomization to the first documentation of disease progression, death due to any cause, or receipt of subsequent anticancer therapy, whichever occurs first. Receipt of post treatment consolidative radiotherapy, or post treatment chemotherapy for the purpose of mobilizing PBSCs, or ASCT will not be considered to have started new anticancer therapy. Specifically,

$$\text{PFS} = \text{Date of first documented progression, receipt of subsequent anticancer therapy or death} - \text{Date of randomization} + 1.$$

For patients who have not experienced a PFS event, the censoring date is defined as the last date on which progression status was adequately assessed. The primary PFS analysis will be

performed for mITT set based on the investigator assessment. The primary PFS will be censored based on FDA guidance and is described in Table 1.

Table 1: PFS Event Rules for Primary PFS Analysis (Investigator Assessment)

Situation	Date of Progression or Censoring	Outcome
No baseline and/or post-baseline assessment	Date of randomization	Censored
Documented progression	Date of documented progression ^a	Event
New anticancer therapy initiated prior to documented progression with the exception of post treatment consolidative radiotherapy, or post treatment chemotherapy for the purpose of mobilizing PBSCs, or ASCT	Start date of new anticancer therapy	Event
Investigator claim of clinical progression without documented progression	Date of investigator claimed clinical progression	Event
Death before first documented progression and new anticancer therapy	Date of death	Event
No progression, new anticancer therapy or death	Date of last adequate assessment ^{a,b}	Censored

a as defined in Section 6.4

b Date of randomization in the absence of post-baseline response assessment

Additional details of censoring rules are as follows:

- Patients who do not have tumor progression or a new anticancer therapy and are still on study at the time of an analysis will be censored at the date of the last disease assessment documenting absence of progressive disease (including physical exam during long-term follow-up)
- Patients who have started post treatment consolidative radiotherapy, palliative radiotherapy, post treatment regimen for the purpose of mobilizing PBSCs, or SCT other than the study treatment prior to tumor progression or new anticancer therapy will be censored at the date of the last disease assessment documenting absence of progressive disease (including physical exam during long-term follow-up)
- Patients who are removed from study prior to documentation of tumor progression or initiation of new anticancer therapy will be censored at the date of the last disease assessment documenting absence of progressive disease (including physical exam during long-term follow-up)

Specifically, censored PFS will be calculated as:

Censored PFS = max (1, last disease assessment date – date of randomization + 1),

Where the last disease assessment date is the date of the last disease assessment obtained during study, or before the initiation of subsequent anticancer therapy (if applicable).

The statistical hypothesis for PFS can be expressed in terms of the hazard ratio $\lambda_{19A+RICE} / \lambda_{RICE}$ where $\lambda_{19A+RICE}$ represents the hazard of progression on the 19A+RICE arm and λ_{RICE} represents the hazard of progression on the RICE arm. A hazard ratio <1 indicates

that the risk of disease progression or death is reduced for patients on the 19A+RICE arm compared with patients on the RICE arm.

The null and alternative hypotheses can be written respectively as:

$$H_0: \lambda_{19A+RICE} / \lambda_{RICE} = 1$$

$$H_A: \lambda_{19A+RICE} / \lambda_{RICE} \neq 1$$

Kaplan-Meier methods will be used to estimate the PFS. The hypothesis test will be performed only if the null hypothesis for the primary endpoint of CR by IRF is rejected. The stratified log-rank test without adjustments for covariates will be used to assess the difference in PFS between 19A+RICE and RICE. The test will be performed using a two-sided, $\alpha=0.1$ level test in the mITT analysis set. All events entered in the database at the time of analysis that have been source data verified will be included in the analysis of PFS. If the test for CR rate per IRF is not statistically significant, the p-value of the tests for PFS will still be calculated, but will be considered descriptive.

Kaplan-Meier Curves depicting PFS in the two arms will be generated. Additionally, median PFS and probability of PFS will be reported at 6 month intervals. The two-sided 90% confidence intervals (CI) for the median will be calculated using the complementary log-log transformation method (Collett 1994).

The primary analysis of PFS will be performed based on investigator assessment. PFS may be performed for each of the subgroups specified in Section 6.8.

Cox regression of PFS will be used to estimate the hazard ratio of 19A+RICE to RICE. The baseline covariates specified in Section 6.9 may be included in the model. The treatment group variable will always be included in the model. Interaction effects may be considered whenever possible.

Secondary Analysis for PFS

The censoring rule for PFS based on IRF assessment is presented in Table 2 as follows:

Table 2: PFS Event Rules for Secondary PFS Analysis (IRF Assessment)

Situation	Date of Progression or Censoring	Outcome
No baseline and/or post-baseline assessment	Date of randomization	Censored
Documented progression documented between scheduled visits	Date of documented progression ^a	Event
New anticancer therapy initiated prior to documented progression or without documented progression or death, with the exception of post treatment consolidative radiotherapy, or post treatment chemotherapy for the purpose of mobilizing PBSCs, or ASCT	Start date of new anticancer therapy	Event
Death before first documented progression and new anticancer therapy	Date of death	Event
No progression, new anticancer therapy or death	Date of last adequate assessment ^{a,b}	Censored

a Determined by IRF based on IRF charter

In this analysis, investigator claim of clinical progression that is not confirmed by IRF assessment at the same visit will not be regarded as having a progression event.

Sensitivity Analyses

Sensitivity analyses of PFS will be performed. Sensitivity analyses may include, but will not be limited to, the following

1. For patients with new anticancer therapy initiated prior to documented progression, PFS will be censored at the date of last adequate assessment prior to the new therapy.
2. An unstratified log-rank test will be used to compare the PFS by investigator between the treatment groups. PFS will be censored according to Table 1. Additionally, an unstratified Cox regression model will be used to estimate the hazard ratio and the corresponding 90% CI for the treatment effect.
3. Stratified log-rank test by stratification factors recorded on the baseline disease diagnosis CRF will be used to compare the PFS by investigator between the treatment groups. PFS will be censored according to Table 1.
4. Allogeneic SCT will not be regarded as an event.

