9.2.2 Secondary Efficacy Endpoints

9.2.2.1 Progression-Free Survival (PFS)

PFS is defined as the time from randomization to first documentation of disease progression per investigator (including progressive metabolic disease by PET/CT or progressive disease by CT as assessed by the Lugano classification criteria ([Cheson 2014](#)), or investigator claim of clinical progression), death due to any cause, or receipt of subsequent anticancer therapy, whichever comes first. Note that patients receiving post-treatment consolidative radiotherapy, post-treatment chemotherapy for the purpose of mobilizing PBSC, or ASCT will not be considered as having started new anticancer therapy.

PFS by IRF may also be evaluated.

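### A PFS censoring bullet in SAP 7.5.2.1 is not limited to event-free patients: as written it contradicts Table 1 and the protocol, and on any reading it leaves allogeneic SCT and palliative radiotherapy unresolved

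*SAP*

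**What the plan says.** The protocol (9.2.2.1) defines PFS as time from randomization to progression, death or subsequent anticancer therapy. It adds that patients receiving consolidative radiotherapy, mobilising chemotherapy "or ASCT will not be considered as having started new anticancer therapy". The SAP definition (7.5.2.1) agrees: such treatment "or ASCT will not be considered to have started new anticancer therapy". The SAP then introduces censoring with "For patients who have not experienced a PFS event, the censoring date is defined as the last date" of adequate assessment, and refers to Table 1 for the primary analysis. Table 1 counts documented progression, clinical progression, death and new anticancer therapy as events, with no exclusion for an earlier ASCT. Apart from patients lacking assessments, it censors only those with none of these.

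Three bullets of additional detail follow Table 1. The second begins "Patients who have started post treatment consolidative radiotherapy, palliative radiotherapy, post treatment regimen for the purpose of mobilizing PBSCs" and continues to "SCT other than the study treatment prior to tumor progression or new anticancer therapy will be censored". The date it assigns is "censored at the date of the last disease assessment documenting absence of progressive disease (including physical exam during long-term follow-up").

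Sensitivity analysis 4 in the same section reads "Allogeneic SCT will not be regarded as an event". SAP 7.5.2.2 offers a similar sensitivity analysis for duration of CR.

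**The concern.** The second bullet has no condition that the patient be free of a PFS event. The first bullet does: it covers patients without progression or new therapy who are still on study. A programmer following the second bullet as written would censor a patient who was transplanted, had a clean scan and then progressed. Table 1 counts that patient as an event.

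The protocol cannot settle the matter on its own, because its section 9.3.1.3 leaves censoring details to the SAP. PFS is the first test after CR in the fixed sequence (SAP 6.8), and ASCT is the aim of salvage treatment here, so many patients could be affected. None of the listed PFS sensitivity analyses compares the two ways of handling ASCT.

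**Working it through.** **1. Side by side.**

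| Situation | Definition and Table 1 | Bullet 2, literal | Bullet 2, event-free patients only |
|---|---|---|---|
| Progression or death after ASCT, mobilisation or consolidative RT | Event | Censored | Event |
| Same treatments, no event | Censored at last adequate assessment | Censored at last progression-free assessment | Same as Table 1 |
| Allogeneic SCT | Not among the exemptions; sensitivity analysis 4 implies an event | Censored (unrestricted SCT) | Censored |
| Palliative RT | Not among the exemptions; an event only if it is new anticancer therapy, which is not defined | Censored | Censored |

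The first row is a conflict only on the literal reading. The last two rows stay unresolved on both.

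**2. The plan's own figure.** The only stated power is for CR: 60% vs 35%, about 50 per arm, two-sided alpha 0.1, about 80%. Power = Φ{[0.25√50 − 1.645√(2 × 0.475 × 0.525)] / √(0.60 × 0.40 + 0.35 × 0.65)} = Φ{(1.768 − 1.162)/0.684} = Φ(0.886) = 81.2%. This reproduces. No hazard ratio, event count or power is given for PFS, so what follows is illustration.

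**3. Events at stake on the literal reading.** Protocol 1.1 cites 50% of patients reaching ASCT in one trial. It also cites 3-year PFS of 81% or 35% after a negative or positive pre-transplant PET in another study. With 100 patients, post-ASCT events by 3 years number between 100 × 0.5 × (1 − 0.81) = 9.5 and 100 × 0.5 × (1 − 0.35) = 32.5.

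With half the patients transplanted and none of them able to have an event, at most 50% could have a PFS event. The 70% trigger for an early PFS analysis (SAP 6.11) could then not be reached.

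**4. Loss of events alone.** Schoenfeld power = Φ(|ln HR|√D/2 − 1.645). At an assumed HR of 0.6, D = 70 gives Φ(0.492) = 69% and D = 50 gives Φ(0.161) = 56%. This holds the HR fixed, which step 5 shows is not safe.

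**5. Simulation.** 50 per arm and 1,500 runs per scenario. Assumptions: median PFS without ASCT 4 months in both arms, ASCT at day 98, accrual over 24 months, cutoff 24 months after last enrolment. The literal rule censors each transplanted patient at the last scheduled clean visit. Only transplant is modelled, not mobilisation or radiotherapy. Pairs are RICE / 19A+RICE.

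| ASCT rate | Post-ASCT 3-year PFS | Events, Table 1 → literal | Median HR | Significant in favour of 19A+RICE |
|---|---|---|---|---|
| 50% / 50% | 35% / 81% | 69.3 → 49.7 | 0.64 → 0.91 | 58% → 10% |
| 50% / 50% | 50% / 65% | 69.5 → 49.8 | 0.87 → 0.96 | 16% → 7% |
| 50% / 65% | 58% / 58% | 64.8 → 42.3 | 0.75 → 0.62 | 31% → 44% |
| 50% / 65% | 65% / 35% | 70.3 → 42.4 | 1.11 → 0.69 | 2% → 33% |
| 50% / 50% | 58% / 58% | 69.1 → 49.6 | 1.01 → 1.00 | 5% → 5% |

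The share of events lost runs from (69.1 − 49.6)/69.1 = 28% to (70.3 − 42.4)/70.3 = 40%. In the last row, with no arm difference, two-sided rejection is 10.4% and 10.1%.

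A second model used non-ASCT PFS of 2 months plus an exponential with mean 4 months, post-ASCT 3-year PFS of 60% in both arms, and 24 to 42 months of follow-up. It lost 17 to 19 of 63 to 67 events (25% to 29%). With ASCT in 45% / 65% the HR moved from 0.66 to 0.55 and rejection from 49% to 64%.

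**The case against.** The strongest reply is that the literal reading is the least natural one. The bullets elaborate a sentence that assigns censoring dates only to patients without an event, and Table 1 is named as the governing rule. The third bullet points the same way. It censors patients removed from study before progression, and death is a listed reason for leaving the study (protocol 4.3.2), so read literally it would censor deaths that Table 1 counts. Protocol 6.7 schedules PFS visits after ASCT, and sensitivity analyses 2 and 3 cite Table 1. This stands as evidence of intent, and on that reading the ASCT conflict disappears. The bullet does not say so, however, and allogeneic SCT and palliative radiotherapy remain.

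Four stronger inferences are tempting and are not supported:

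- *That patients are censored at transplant.* The date is the last progression-free assessment, which may fall well after ASCT.
- *That the bias favours 19A+RICE.* It does so only under some assumptions. When post-ASCT outcome favours 19A+RICE and transplant rates are equal, the literal rule moves the HR towards 1. With no arm difference there is no type I inflation.
- *That duration of CR and of objective response carry the same fault.* SAP 7.5.2.2 ties duration of CR to Table 1, not to the bullets, and 7.5.2.5 follows 7.5.2.2.
- *That Table 1 makes palliative radiotherapy an event.* It does so only if palliative radiotherapy is new anticancer therapy, a term left undefined. Simply deleting it from the bullet would leave its status open.

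The event status of allogeneic SCT is also inferred, from the sensitivity analyses in SAP 7.5.2.1 and 7.5.2.2. The protocol is mixed: section 3.1 exempts stem cell transplant without qualification when saying how long assessments continue, and 9.2.2.4 and 9.2.2.5 set aside both transplant types for other endpoints.

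**Conclusion.** The bullet is wrong as written and should be fixed. Literally applied, it contradicts the PFS definition, Table 1 and protocol 9.2.2.1, and would censor later progressions and deaths in transplanted patients. That is roughly a quarter of PFS events in the illustrations, and up to 40% where 65% of one arm is transplanted and does worse afterwards. The HR could be distorted in either direction, depending on arm differences in ASCT rate and post-ASCT outcome.

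These sizes rest on assumed arm-specific ASCT rates and PFS curves. The 50%, 81% and 35% are background figures in the protocol, not design inputs. On the event-free reading the main effect vanishes, and two narrower gaps remain: allogeneic SCT and palliative radiotherapy. The matter concerns a key secondary endpoint that is formally tested only if CR is significant.

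**What to change.** Replace the second bullet with a rule to this effect: consolidative radiotherapy, chemotherapy to mobilise PBSC, and ASCT are neither events nor reasons for censoring; later progression, death or new anticancer therapy is the event; only patients with no PFS event are censored, at the last adequate assessment. Write ASCT in place of SCT.

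State explicitly in Table 1 whether palliative radiotherapy and allogeneic SCT count as new anticancer therapy in the primary PFS analysis, and keep that consistent with sensitivity analysis 4.

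The cost is SAP wording only and needs no new data. Because the trial is open-label, the change should be made before database lock, so that the rule is not chosen with results in view.

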7.5.2.2 Duration of Complete Remission

Duration of complete remission (CR) is defined as the time from start of the first documentation of CR to the first documentation of disease progression, new anticancer therapy or to death due to any cause, whichever comes first. Note that receipt of post treatment consolidative radiotherapy, post treatment chemotherapy for the purpose of mobilizing PBSCs, or consolidative autologous SCT will not be considered to have started new anticancer therapy.

The analysis for the duration of CR will be performed for patients in mITT set who achieved CR at EOT based on investigator assessment. The censoring of the duration of CR will follow the censoring rule for PFS based on the investigator assessment in Table 1. The secondary analysis for duration of CR will be based on IRF assessment as specified in Table 2. If a patient received subsequent allogeneic SCT, a sensitivity analysis may be performed and allogeneic SCT will not be regarded as an event.

Kaplan-Meier methodology will be used to analyze duration of CR. The median time and its two-sided 90% CI using the log-log transformation method (Collett 1994) will be calculated when appropriate. Kaplan-Meier plots for the two treatment groups will be provided.

A stratified log-rank test without adjustment for covariates will be used in the evaluation of differences between the treatment arms in the mITT analysis set when appropriate. If the p-values for the analyses of CR and PFS are not statistically significant, the p-value for duration of CR will be descriptive.

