9 DATA ANALYSIS METHODS

9.1 Determination of Sample Size

With approximately 100 patients randomized in a 1:1 ratio to each treatment arm (~50 patients per arm), the study is designed to have approximately 80% power to detect an increase in the CR rate of 25%. It is assumed that the CR rates for the 19A+RICE Arm and the RICE Arm are 60% and 35%, respectively. This calculation is based on a two-sided χ^2 test with significance level of $\alpha=0.1$ using EAST (version 5.4).

If the dose of denintuzumab mafodotin in the investigational 19A+RICE arm is modified, up to 50 additional patients may be randomized (25 in each arm) so that a total of 100 patients will be randomized in a 1:1 ratio to either the 19A (modified dose) + RICE arm or the RICE only arm. Up to approximately 150 patients may be randomized in this study. If a subset of patients appears to potentially derive benefit from 19A+RICE versus RICE at a pre-planned evaluation, the Sponsor may continue enrolling those patients beyond the planned sample size (approximately 100 patients), but will not exceed the planned maximum number of patients to be randomized in this study (up to approximately 150 patients).

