9.3.1.5 Multiple Comparisons and Multiplicity

The overall two-sided alpha level for the primary endpoint is 0.1.

Formal statistical tests will be performed for the CR per IRF, and the key secondary endpoints of PFS and duration of CR. If the test for the primary analysis of CR rate is statistically significant in favor of the investigational arm at a two-sided alpha level of 0.1, formal statistical tests will be performed for the key secondary endpoints at an overall two-sided alpha level of 0.1. A fixed sequence testing procedure, where testing is carried out sequentially at an unadjusted alpha level as long as all preceding null hypotheses are rejected, will be used to ensure type I error control for key secondary endpoints. The testing order will be: 1) PFS, and 2) duration of CR. If the test for CR rate per IRF is not statistically significant, the p-value of the tests for the key secondary endpoints will still be calculated, but will be considered descriptive.

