6.8 Multiple Comparison/Multiplicity

A fixed sequence testing procedure (Westfall 2001), where testing is carried out sequentially at an unadjusted alpha level as long as all preceding null hypotheses are rejected, will be used to ensure type I error control for key secondary endpoints. The testing order will be: 1) CR rate per IRF; 2) PFS per investigator assessment; and 3) duration of CR per investigator assessment. If the test for CR rate is not statistically significant, the p-value of the tests for the subsequent endpoints will still be calculated, but will be considered descriptive.

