6.9 Examination of Subgroups

As exploratory analyses, subgroup analyses may be conducted for selected endpoints. Subgroups may include but are not limited to the following:

- Disease status ([CR to frontline systemic therapy and relapsed >12 months after initial diagnosis] versus [PR or SD to frontline systemic therapy, or CR to frontline and relapsed ≤12 months after initial diagnosis])
- Disease risk as determined by standard IPI or saalPI
- Disease type (De novo DLBCL/G3bFL versus Transformed DLBCL)
- Cell of origin by gene expression profiling (GEP)
- Double- and triple- hit lymphoma
- Double expresser lymphoma
- CD19 expression
- CD20 expression
- Minimum Residual Disease (MRD) status
- Age (18- 64 vs. ≥ 65years; and/or < 60 vs >60 years)
- Gender
- Baseline ECOG
- Disease stage
- Patients with and without post-baseline consolidative ASCT

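### Duration of CR is formally tested between arms among complete responders only, a comparison that randomisation does not protect

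*SAP*

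**What the plan says.** Protocol 9.3.1.5 makes PFS and duration of CR key secondary endpoints with formal tests once CR rate is significant in favour of 19A+RICE: "The testing order will be: 1) PFS, and 2) duration of CR". SAP 6.8 writes the same sequence with CR rate per IRF first, PFS second and, last, "3) duration of CR per investigator assessment". Each step uses an unadjusted two-sided 0.1.

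SAP 7.5.2.2 defines who is compared: "The analysis for the duration of CR will be performed for patients in mITT set who achieved CR at EOT based on investigator assessment". The arms are compared by a stratified log-rank test without covariates. That test sentence mentions the mITT set, but this does not widen the comparison: the clock starts at first CR, so a patient without CR has no duration.

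If CR rate or PFS is not significant, the duration-of-CR p-value is descriptive. SAP 6.8 says that p-values for the later endpoints are still calculated when CR rate fails. Neither document says that the responder groups are not a randomised comparison, and neither plans an all-patient alternative for this endpoint.

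**The concern.** The trial is designed to change who reaches CR: "It is assumed that the CR rates for the 19A+RICE Arm and the RICE Arm are 60% and 35%, respectively". The formal duration test is reached only after CR rate and PFS have both differed between arms. That is when the responder groups are least likely to be alike.

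Suppose 19A+RICE converts some patients who would have failed RICE. Its responder group then contains a type of patient that is missing from the RICE responder group. If those patients relapse sooner, the drug looks worse on durability; if later, it looks better. Either can happen although no patient who would respond on either arm has a longer or shorter remission. A significant result in the last slot would be read as a treatment effect on durability when it may only reflect a change in who responds.

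**Working it through.** **1. The plan's own figure.** Inputs from Protocol 9.1 and 9.3.1.5: 50 per arm, CR 60% vs 35%, two-sided alpha 0.1. Pooled SE under the null: sqrt(2 × 0.475 × 0.525 / 50) = 0.0999. SE under the alternative: sqrt(0.35 × 0.65/50 + 0.60 × 0.40/50) = 0.0967. Power = Φ[(0.25 − 1.645 × 0.0999)/0.0967] = Φ(0.886) = 0.81. Exact enumeration of the chi-square test gives 0.80. The stated 80% is reproduced.

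**2. Who enters the duration test.** 50 × 0.60 = 30 and 50 × 0.35 = 17.5 patients. If every RICE responder would also respond on 19A+RICE, the extra responders are (60 − 35)/60 = 42% of the 19A+RICE group.

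**3. When the test is reached.** With 17.5/50 control CRs, the smallest significant 19A+RICE count is 26/50, a difference of 17 points: 0.17/sqrt(2 × 0.435 × 0.565/50) = 1.71 > 1.645. So the formal test follows only a sizeable CR difference, and PFS must then pass too.

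**4. Illustration.** Assumed, not given by the documents for this purpose:
- exponential times and follow-up of 24-42 months;
- median PFS without CR of 4 to 12 months;
- a 3-year remission rate of 81% in common responders (those who reach CR on either arm), identical on both arms;
- a 3-year rate in the extra responders that is varied;
- unstratified tests, 50 per arm.

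The 3-year rate among 19A+RICE responders is (35 × common + 25 × extra)/60. For extra = 35% it is (35 × 0.81 + 25 × 0.35)/60 = 62%, against 81% among RICE responders.

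| 3-year rate, extra responders | 19A+RICE responders | RICE responders | Ungated test: worse | Formal worse, after CR and PFS pass |
|---|---|---|---|---|
| 35% | 62% | 81% | 37-39% | 2-8% |
| 50% | 68% | 81% | 21-22% | 2-6% |
| 65% | 74% | 81% | 11-12% | 2-3% |
| 81% | 81% | 81% | 4% | 1-2% |

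The nominal rate is 5% per direction. Ranges cover the assumed PFS without CR; repeat runs move the entries by a point or two.

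**5. The other direction.** With common responders at 50% and extra responders at 81%, the 19A+RICE responder rate is (35 × 0.50 + 25 × 0.81)/60 = 63% against 50%. A formal better finding then occurs in about 16-17% of trials.

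**6. A second set of assumptions.** Here there are 24 months' accrual, 24 months' further follow-up, a median PFS without CR of 4 months and a median CR duration of 24 months in common responders. If extra responders have a median of 6, 12, 24 or 48 months, the 19A+RICE responder median becomes 12.7, 17.7, 24.0 or 31.4 months. The ungated test says worse in 37%, 18%, 4% and 1% of trials, and better in 0.3%, 1%, 6% and 17%. A formal worse finding occurs in at most 0.5%. With equal CR rates the ungated test keeps its size (5.0% worse, 5.4% better).

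**7. What an all-patient measure shows.** Take medians of 24 months (common) and 6 months (extra). Mean time in CR over the 24 months after CR begins is (m/ln 2)(1 − 2^(−24/m)), which is 17.3 and 8.1 months. Counting 0 for patients without CR, RICE has 0.35 × 17.3 = 6.1 months and 19A+RICE has 6.1 + 0.25 × 8.1 = 8.1. Among responders only, the order reverses: 8.1/0.60 = 13.5 months against 17.3.

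**The case against.** The strongest reply is that the hierarchy already guards the formal claim. PFS compares whole mITT arms and must pass first. When extra remissions are short, PFS often fails, so most misleading duration results never become formal. This stands, and it cuts the size of the problem a good deal. A reader might take the ungated 37-39% as the chance of a formal wrong-direction finding. The documents do not support that, because the sequence requires both CR rate and PFS to be significant; the formal figure is about 2-8%. The gate protects less well against a spurious better finding, and it leaves the Kaplan-Meier curves, medians and descriptive p-value as they are.

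A reader might also treat 35% as the protocol's figure for the extra responders. It is not. Protocol 1.1 reports 81% and 35% as 3-year PFS in patients with a negative and a positive pre-transplant PET scan. Extra responders are complete responders, and on PET a CR is a negative scan. The 35% row is therefore an extreme case, which is why a range is shown.

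It would also go too far to say that type I error control has no meaning here. With equal CR rates, or equal prognosis among the extra responders, the test keeps about its nominal size. Because it is last, an error there cannot affect CR rate or PFS.

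Finally, a reader might extend the point to the listed subgroup "Patients with and without post-baseline consolidative ASCT". That analysis is optional and exploratory, and Protocol 9.3.1.8 presents all analyses by treatment arm. Any bias from comparing transplanted with non-transplanted patients is a separate question, and neither document says that this comparison will be made.

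**Conclusion.** The point holds. A formally tested key secondary endpoint is compared within a post-randomisation subset that the trial is designed to enlarge from 35% to 60%, and nothing elsewhere in the plan repairs this. The sequence controls error for a hypothesis about responder groups, not for a treatment effect on remission length.

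The size is moderate and conditional. It depends on the extra responders having a different prognosis, and on remission times, follow-up and PFS without CR that the documents do not give. The 42% share further assumes that every RICE responder would also respond on 19A+RICE. The conclusions on CR rate and PFS are unaffected.

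**What to change.** - Protocol 9.3.1.5 and SAP 6.8: end the fixed sequence at PFS.
- SAP 7.5.2.2: report duration of CR by arm as Kaplan-Meier estimates with 90% CI, labelled a non-randomised description of responders. Remove the between-arm log-rank test and its p-value, including the descriptive one.
- If durability must be compared, define time in CR from randomisation, with 0 for patients without CR. Analyse it over the whole mITT set, which is the plan's testing population.

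There is no need to fill the vacated slot with another endpoint such as OS. That would be a design choice needing its own power justification.

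The cost is SAP wording and one protocol sentence. Protocol 9.3 requires an amendment for an analysis change only if site conduct alters, so the change can be made in the SAP before database lock and recorded in SAP 9.1. The downside is that the sponsor gives up a formal duration-of-CR claim.
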